 - **UKK.** University Hospital of Cologne (Germany)
 - **MSD.** Merck Sharp & Dohme (United States)

 EPAD - 115736	D2.11 Master Statistical Analysis Plan for the EPAD Platform Proof-of-Concept Trial		
	WP2. Statistical/Methodology Engine Room	Version: v2.0 – Final	
	Author(s): [name], [name], [name]	Security: PU	7/36

- **Grant Agreement.** The agreement signed between the beneficiaries and the IMI JU for the undertaking of the EPAD project (115736).
- **Project.** The sum of all activities carried out in the framework of the Grant Agreement.
- **Work plan.** Schedule of tasks, deliverables, efforts, dates and responsibilities corresponding to the work to be carried out, as specified in Annex I to the Grant Agreement.
- **Consortium.** The EPAD Consortium, comprising the above-mentioned legal entities.
- **Project Agreement.** Agreement concluded amongst EPAD participants for the implementation of the Grant Agreement. Such an agreement shall not affect the parties' obligations to the Community and/or to one another arising from the Grant Agreement.

 EPAD - 115736	D2.11 Master Statistical Analysis Plan for the EPAD Platform Proof-of-Concept Trial		
	WP2. Statistical/Methodology Engine Room	Version: v2.0 – Final	
	Author(s): [name], [name], [name]	Security: PU	8/36

EXECUTIVE SUMMARY

The purpose of the EPAD Proof-of-concept (PoC) Platform Trial Protocol is to study multiple interventions for the secondary prevention of Alzheimer’s dementia in people with prodromal or preclinical Alzheimer’s disease. This document is the corresponding Statistical Analysis Plan (SAP). As the PoC Platform Trial was not initiated, the SAP has not been finalized. The role of this document is to make the material available for future use. Consequently, it has not been a priority to make the document have a finished appearance. In other words, the document includes unfinished parts.

As a master SAP, a key point is to describe the data sharing between the Intervention-specific trials and the consequences of this sharing. A second point is to describe the common methods, in particular, the interim analyses used to decide on whether the trials stop or continue. Each Intervention Specific Trial will have a dedicated SAP.

Each intervention specific trial will have interim analyses for efficacy made every 3 months, after 50 research participants have reached 12 months of follow-up. The primary endpoint is RBANS total score. The dataset for the analysis consists of all available data for the research participants in the intervention specific trial supplemented with placebo data from the other intervention specific trials within the relevant strata. The model is a Bayesian disease progression model, where the placebo group has an arbitrary development over time, in each of the up to four strata recruiting to the trial. The active treatment group is assumed to show a change from baseline multiplied by a common factor (CPRR: Cognitive Progression Rate Ratio), so a value below 1 means that the disease progression is delayed. If an interim analysis shows that the posterior probability of $CPRR < 0.90$ is greater than 0.85, the intervention meets the success criterion. If the posterior probability of $CPRR < 0.90$ is less than 0.05, the intervention is declared futile.

 EPAD - 115736	D2.11 Master Statistical Analysis Plan for the EPAD Platform Proof-of-Concept Trial		
	WP2. Statistical/Methodology Engine Room	Version: v2.0 – Final	
	Author(s): [name], [name], [name]	Security: PU	9/36

1. List of Abbreviations and Definitions of Terms

AE	Adverse Event
AESI	Adverse Event of Special Interest
Amsterdam-IADL	Amsterdam-Instrumental Activity of Daily Living
AR	Adverse Reaction
CDR-GS	Clinical Dementia Rating Scale Global Score
CDR-SB	Clinical Dementia Rating Scale- Sum of Boxes
CSF	Cerebro-Spinal Fluid
C-SSRS	Columbia–Suicide Severity Rating Scale
DSMB	Data Safety Monitoring Board
EPAD	European Prevention of Alzheimer’s Disease
FSFV	First Subject First Visit (baseline) of the relevant IST
GDS	Geriatric Depression Scale
IDMC	Independent Data Monitoring Committee
ISA	Intervention Specific Appendix
ISA-POC	Intervention-specific Appendix Statistical Analysis Plan
IST	Intervention Specific Trial
LCS	Longitudinal Cohort Study
LSFV	Last Subject First Visit (baseline) of the relevant IST
MRI	Magnetic Resonance Imaging
NIH-EXAMINER	National Institutes of Health-Executive Abilities: Measures and Instruments for Neurobehavioral Evaluation and Research
PoC	Proof of Concept
PSC	PoC Steering Committee
PSQI	Pittsburgh Sleep Quality Index
RBANS	Repeatable Battery for the Assessment of Neuropsychological Status
RP	Research Participant
SAE	Serious Adverse Event
SAP	Statistical Analysis Plan
STAI	State-Trait Anxiety Inventory
TIA	Cerebrovascular accident (stroke and/or transient ischemic attack)
WML	White Matter Lesion

 EPAD - 115736	D2.11 Master Statistical Analysis Plan for the EPAD Platform Proof-of-Concept Trial		
	WP2. Statistical/Methodology Engine Room	Version: v2.0 – Final	
	Author(s): [name], [name], [name]	Security: PU	10/36

2. INTRODUCTION

EPAD (European Prevention of Alzheimer’s Disease) is a project to develop an environment for studying Alzheimer’s disease and then test multiple different interventions for the secondary prevention of Alzheimer’s dementia in people with prodromal or preclinical Alzheimer’s disease. The EPAD project is running across Europe with multiple partners from academia and the commercial sector.

The project is designed as a perpetual platform trial. This implies that there is a single Master Protocol dictating the conduct of the trial. The specific protocol for each intervention or combination of interventions that enters the platform trial is summarized by an Intervention Specific Appendix (ISA) to the Master Protocol. Each intervention specific trial is inferentially separate, meaning that conclusions and reports are done separately even though some placebo treated research participants may contribute to several such reports. Thus, there will not be considerations of type I error across intervention specific trials.

The overarching statistical analysis considerations of the trial are dictated in a single Master Statistical Analysis Plan (SAP) – this document. The specific SAP for each intervention specific trial is summarized by an appendix to the master SAP. In case of conflicting information between the Master SAP and the ISA, the ISA should be heeded.

An overview of the terminology is given in the table below

Generic name	Name in full trial	Name in substudy
Clinical trial	POC Platform trial	Intervention specific trial (IST) (Master protocol calls this Intervention-specific Appendix)
Protocol	Master protocol	Intervention-specific Appendix (ISA)
Statistical Analysis Plan	Master SAP (SAP)	Intervention-specific Appendix Statistical Analysis Plan (ISA-SAP)
Subject	Research Participant (RP)	Intervention specific trial participant
Population	Trial population	Intervention specific trial population (Master protocol calls this Intervention Cohort)
Interim analysis	- (not applicable)	Interim analysis (Master protocol calls this evolution analysis)

 EPAD - 115736	D2.11 Master Statistical Analysis Plan for the EPAD Platform Proof-of-Concept Trial		
	WP2. Statistical/Methodology Engine Room	Version: v2.0 – Final	
	Author(s): [name], [name], [name]	Security: PU	11/36

Three kinds of analyses will be performed: Interim analyses for the Independent Data Monitoring Committee (IDMC), interim analyses for the Data Safety Monitoring Board (DSMB) and final analyses. The below is trying to cover all three kinds. No calculations will involve unblinded data from active treatments from several ISTs unless agreed by all owners of compounds involved in the calculation. Interim analyses will be done every three months; at the same time for all ongoing ISTs but as said above there will be separate analyses for each IST; involving all research participants from the relevant substudy and selected placebo research participants from other ISTs (details described in Section 7). For each IST, there will be one final analysis, which is done, when all Intervention specific trial participants have reached the safety follow-up visit. As concurrent placebo research participants may continue to participate after end of an IST, the exact cut-off date will be decided in each case.

3. Responsibilities

Final analysis: IQVIA

Interim analyses for IDMC: IQVIA using software provided by Berry Consultants. There is one IDMC handling the master trial.

Interim analyses for DSMB: IQVIA. There is one DSMB handling the master trial.

4. Objectives

The ISA may add objectives referring to the IST.

4.1. Primary objective(s)

The primary objective of this clinical trial is to assess the efficacy and safety of multiple interventions compared to placebo, in research participants showing evidence of preclinical to prodromal Alzheimer's disease for the secondary prevention of Alzheimer's dementia. The interventions can be tested simultaneously, with the potential for new interventions to be added sequentially, and perpetually. The primary objective of the trial is to evaluate the potential for a reduction in the rate of clinical decline as measured by the primary cognitive clinical endpoint.

4.2. Secondary objective(s)

The secondary objectives of the trial are to evaluate the potential for a reduction in decline or improvement in the specific cognitive domains as measured by the secondary cognitive outcomes (RBANS domains and other cognitive endpoints) as well as reduction in decline or improvement in the biological and other clinical endpoints.

 EPAD - 115736	D2.11 Master Statistical Analysis Plan for the EPAD Platform Proof-of-Concept Trial		
	WP2. Statistical/Methodology Engine Room	Version: v2.0 – Final	
	Author(s): [name], [name], [name]	Security: PU	12/36

4.3. Exploratory objective(s)

The exploratory objectives of the trial are to evaluate the potential for a reduction in decline or improvement in the specific cognitive domains as measured by the exploratory cognitive outcomes as well as reduction in decline or improvement in the biological and other clinical endpoints.

4.4. Safety objectives(s)

The safety of an intervention will be monitored throughout the trial.

5. Study Design

This is a multi-centre, multi-national, double-blind, randomized, placebo-controlled, adaptive, perpetual platform clinical trial to investigate the efficacy and safety of multiple drugs simultaneously or sequentially.

There will be multiple interventions, where the research participants on an intervention and its specific blinded placebo are labelled as the intervention specific trial population. Intervention specific trial populations may start at different time points in the course of the trial. Therefore, the double-blind will be maintained within an intervention specific trial population between the different arms in that cohort. Research participants will not be blinded to which intervention specific trial they participate in. For an intervention specific trial, the number of intervention arms versus placebo will be defined in the Intervention Specific Appendix. The randomization ratio within each intervention specific trial is 3:1 (total active arms: placebo). Each intervention arm within an intervention specific trial is labelled as a subarm.

This adaptive platform design will utilise common control research participants from multiple intervention specific trials and common minimum success and futility criteria evaluated at the interim analyses. The ISA may describe further adaptive features, referring to the IST, such as changes in allocation ratios for the active arms, when there are multiple active arms

Research participants who have been enrolled in the LCS for the below minimum time points will be invited to participate in the PoC trials (note that the criteria referring to CSF may have been assessed at an earlier time point):

1. For prodromal research participants they have completed Visit 2/Month 6 procedures in the EPAD LCS.
2. For preclinical research participants they have completed Visit 3/Month 12 procedures in the EPAD LCS.

The allocation procedure is illustrated in Figure 1. Research participants who provide consent at the transition visit will have an eligibility check done and then be randomly allocated to one of the ongoing Intervention-specific Trials in the EPAD PoC trial for which they are eligible. The participant will be informed of this allocation and provided with written information specific to the IST, then subject to consent they will begin screening procedures for the IST.

 EPAD - 115736	D2.11 Master Statistical Analysis Plan for the EPAD Platform Proof-of-Concept Trial		
	WP2. Statistical/Methodology Engine Room	Version: v2.0 – Final	
	Author(s): [name], [name], [name]	Security: PU	13/36

If eligibility criteria are fulfilled, they will then be randomized on a 3:1 ratio to the intervention active arm or placebo. If there are subarms for an intervention (doses, frequency) then a further randomization would determine the subarm.

In case of a screening failure, participants can be re-randomized as follows:

- Participants who fail to meet eligibility criteria for the Master Protocol will have the possibility to continue to be followed in the LCS until they are eligible for the PoC Platform Clinical Trial Master Protocol
- Participants who fail to meet eligibility criteria during the screening of an intervention will have the possibility to be re-assigned to another intervention for which they are eligible (except see below)
- Participants assigned to an intervention but who withdraw consent for personal reasons (eg, inconvenience of the intervention, mode of administration, etc.) will not be re-assigned to another intervention for 12 months. If a second withdrawal of consent after randomization to the Master Protocol occurs, the subject will be permanently discontinued from the EPAD studies including LCS.

The duration of treatment for each intervention, the follow-up period and the end of the intervention-specific trial will be described in the Intervention Specific Appendix. On the participant level, the trial duration can be up to four years.

At minimum, on-site visits will occur every 3 months during the first year and every 6 months for the remaining years of the trial.

The primary and secondary clinical outcomes will be assessed for all interventions every 6 months. More frequent assessments are discouraged because of the potential learning effects, which could lead to discrepancies between different assessments and therefore a potential bias in the results.

Evolution analyses will take place quarterly within the platform trial. At each of these evolution analyses a set of possible evolutions or adaptations that an intervention is eligible for will be checked.

[figure not shown]
1. An intervention can be found to be successful at modifying the progression of cognitive disease, which will be termed graduation. In this case the sponsor or responsible party will be informed of the successful graduation of the intervention. Upon meeting the criteria for success, no further subjects will be randomized in that IST, but subjects already in that IST may continue for the full, prespecified duration of treatment, if the ISA dictates continuing exposure. The ISA may also specify that exposure is halted upon success.
2. An intervention can be found to have failed to modify the progression of disease and be deemed futile. Upon meeting the criteria for futility, enrolment in that IST would be discontinued for that and all research participants in that IST (including placebo) would discontinue intervention use. Subjects may return to EPAD-LCS or after washout to another intervention if eligible.
3. Maximum exposure may be reached for an intervention. This implies the maximum time of follow-up for all research participants in an arm has been reached. In this case this is the end of the study for that intervention and all research participants in the respective IST would have completed treatment.

 EPAD - 115736	D2.11 Master Statistical Analysis Plan for the EPAD Platform Proof-of-Concept Trial		
	WP2. Statistical/Methodology Engine Room	Version: v2.0 – Final	
	Author(s): [name], [name], [name]	Security: PU	14/36

If an IST has multiple subarms then adaptive rules dictating the behaviour of these arms can be conducted. This can include stopping subarms, evolving subarms, and changing randomization probabilities among subarms. This will be detailed in the Intervention Specific Appendix.

Patients who are withdrawn from treatment will be followed-up; Visit 13 (see Master protocol) should be performed for all research participants who permanently discontinue the IST or complete their treatment period.

Figure 1. Scheme of randomisation process.

 EPAD - 115736	D2.11 Master Statistical Analysis Plan for the EPAD Platform Proof-of-Concept Trial		
	WP2. Statistical/Methodology Engine Room	Version: v2.0 – Final	
	Author(s): [name], [name], [name]	Security: PU	15/36

6. Definitions

Baseline: unless otherwise specified in the ISA, the value captured at Visit 2 (Day 1), before first dose.

Screening period 1: Screening period for the PoC trial Master Protocol. The research participants in the LCS eligible for the PoC trial will be contacted to enter the trial based on eligibility criteria of the Master Trial Protocol. The research participants should be enrolled in the LCS for at least 6 months prior to the screening visit (Visit 1). Screening period 1 starts at Visit 1 and ends at Visit 2.

Screening period 2: Screening period for an Intervention Specific Trial. At Visit 1, the research participant and the study partner will have to consent to participate to one specific intervention for which the research participant is eligible. Screening period 2 starts at Visit 1 and ends at Visit 2.

Treatment period: active treatment period for the intervention specific trial. Starts at Visit 2. The duration of the treatment period will be specified in the ISA.

Follow-up period: safety follow-up period for the intervention specific trial. The duration of the safety follow-up period will be specified in the ISA.

Withdrawal: A patient who withdraws from the study during the treatment period. Patients that complete the treatment period are considered completers.

7. Trial Endpoints

An intervention specific Appendix may choose to upgrade secondary or exploratory endpoints. This will have to be described in the Intervention Specific Appendix and approved by the Appendix Steering Committee.

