This section covers only the final analysis. The interim analyses are similar with additional description in Section 18.1. This section is not completely final. More work is needed regarding the details of the approach. Besides, the assumptions need justification.

The primary efficacy analyses are based on a Bayesian cognitive progression model (BCPM). This cognitive progression model incorporates the following aspects:

- Repeated measures for the cognitive endpoint over the recurring 6-month visit schedule, including pre- and post-intervention
- Patient-level random effect
- Proportional treatment effect for slowing of disease progression rate. If there are several active treatment arms, the ISA will describe how this will be modelled.

Let a cognitive endpoint at visit j for research participant i be labelled Y_{ij} , for $j = \dots, -1, 0, 1, 2, \dots$. The reference to negative visits corresponds to cognitive endpoint values from the LCS study, pre-intervention. The Y_{i0} observation corresponds to the baseline visit at the time of the start of intervention. Visits $j=1,2,3$, refer to the post baseline, on treatment visits (each 6-months separated). Within a specific subgroup, the cognitive progression model is

 EPAD - 115736	D2.11 Master Statistical Analysis Plan for the EPAD Platform Proof-of-Concept Trial		
	WP2. Statistical/Methodology Engine Room		Version: v2.0 – Final
	Author(s): [name], [name], [name]		Security: PU

$$Y_{ij} = \begin{cases} \gamma_i + \sum_{v=j}^{-1} \alpha_v + \epsilon_{ij} & j = \dots, -2, -1 \\ \gamma_i + \epsilon_{ij} & j = 0 \\ \gamma_i + \exp(\theta_{t_i}) \sum_{v=1}^j \alpha_v + \epsilon_{ij} & j = 1, 2, 3 \dots \end{cases}$$

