18.1. Interim analyses for the IDMC

The POC Trial as such will not control for the Type I error. For each IST, the sample size and the stopping criteria are set in consideration of the Type I error, which is evaluated by simulation.

The interim analyses will be conducted every three months. It will be the same time for all ISTs, but the analyses will be made separately. The actual analysis will follow the principles for the primary efficacy analysis described in Section 14.

For each evolution analysis conducted in which an intervention has reached a minimum exposure to research participants, an analysis of graduation (success) will be conducted. With the same constraints, an analysis of futility will be conducted. The default criterion is at least 50 research participants with 12 months of follow up in an intervention cohort, but this can be specified within an ISA. The details of these analyses are:

1. If the posterior probability of a $CPRR < 0.90$ is greater than 0.85 then the intervention meets graduation criteria and will be labelled a success. This analysis concludes a super superiority, meaning there is high probability of at least a 10% slowing in the rate of decline is met for the intervention
2. If the posterior probability of a $CPRR < 0.90$ is less than 0.05 then the futility criteria is met for that intervention. Thus, if there is high probability of less than a 10% slowing in the rate of decline, the intervention will be declared futile.

The sponsor will only be informed of the decision to continue or stop the trial and will not be unblinded to the results until the study has ended.

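### The primary model cannot tell a constant cognitive lift from slower decline, so a drug that slows nothing can graduate as modifying progression

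*Combined protocol and SAP*

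**What the plan says.** Section 4.1 sets the target: "The primary objective of the trial is to evaluate the potential for a reduction in the rate of clinical decline". Section 5 names the success outcome: "An intervention can be found to be successful at modifying the progression of cognitive disease, which will be termed graduation". Section 18.1 reads the success rule, P(CPRR<0.90) above 0.85, as showing a slowing of 10% or more. Futility is the same probability below 0.05.

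The treatment enters the Section 14 model in one way only: "Proportional treatment effect for slowing of disease progression rate". For every visit after baseline, the active mean is exp(θ) times the cumulative placebo change, and CPRR = exp(θ).

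On timing, Section 18.1 says: "The default criterion is at least 50 research participants with 12 months of follow up in an intervention cohort". Section 5 adds: "The primary and secondary clinical outcomes will be assessed for all interventions every 6 months". Participants who have just reached the default trigger therefore have two post-baseline RBANS values. Looks then recur: "The interim analyses will be conducted every three months".

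The re-analyses listed in Section 14 vary the control set, the use of pre-baseline data, calendar time, stratum-specific CPRR and covariates, and they compare control arms. All keep the multiplier. Section 14.1 plans an MMRM, but only for the secondary cognitive endpoints.

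**The concern.** The objective and the success label concern the rate of decline, but the model can express a benefit only as a change in rate. A fixed lift from month 6, with decline parallel to placebo afterwards, has nowhere to go except into the CPRR. Its apparent size depends on follow-up, because a fixed number of points is a large share of a small early decline and a small share of a large late one.

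Two things are at stake. A report could state that decline was slowed when it was not. The same drug could also be judged differently according to when the look falls. On graduation, randomisation into the IST stops and the ISA may halt exposure (Section 5), so later data that would show parallel decline may not be collected.

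**Working it through.** The plan gives no sample size, power or lift to reproduce, so this is an illustration on stated inputs.

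**Inputs**
- From Section 14: between-person SD 12 (variance 144) and prior θ ~ N(0, 0.25²).
- From Annex I (optimiser starting values, the only decline figures in the document): placebo change at 6, 12, 18 and 24 months of −5, −8, −11, −14 (stratum a) and −2, −3, −4, −5 (stratum b); residual variance 25.
- Assumed: decline after 24 months continues at 3 (a) or 1 (b) points per visit; residual variance 81 as a sensitivity value; 300 active and 200 placebo, all with the stated follow-up; a lift of 1.6 points from month 6 with the slope unchanged.

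**Step 1: the lift as a share of placebo decline.** Stratum a: 1.6/8 = 20% at 12 months, 1.6/14 = 11% at 24, 1.6/26 = 6% at 48. Stratum b: 1.6/3 = 53%, 1.6/5 = 32%, 1.6/9 = 18%. The rule looks for 10%.

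**Step 2: what the proportional model fits.** With the placebo change d known, generalised least squares gives CPRR* = 1 + L(d′W1)/(d′Wd). Here 1 marks the post-baseline visits and W is proportional to I − ρJ, where J is the all-ones matrix. For stratum a at 12 months (baseline and two visits), ρ = 144/(25 + 3×144) = 0.315. Then d′W1 ∝ −13 + 0.315×13×2 = −4.81 and d′Wd ∝ 89 − 0.315×13² = 35.7. So CPRR* = 1 − 1.6×4.81/35.7 = 0.78, although the slope ratio is 1.

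**Step 3: posterior.** Visit effects and θ were fitted jointly to the expected means under the SAP prior for θ, with variances fixed, flat priors on the visit effects and a normal approximation. For stratum a at 12 months the fitted CPRR is 0.809 and the posterior SD of θ is 0.081. Hence P(CPRR<0.90) = Φ[(ln 0.90 − ln 0.809)/0.081] = Φ(1.32) = 0.91. The same calculation elsewhere gives:

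| Stratum, residual variance | Fitted CPRR at 12 / 24 / 48 months | P(CPRR<0.90) at 12 / 24 / 48 months |
|---|---|---|
| a, 25 | 0.81 / 0.90 / 0.96 | 0.91 / 0.52 / <0.001 |
| b, 25 | 0.71 / 0.77 / 0.89 | 0.89 / 0.91 / 0.55 |
| a, 81 | 0.83 / 0.90 / 0.96 | 0.74 / 0.53 / 0.03 |
| b, 81 | 0.84 / 0.82 / 0.89 | 0.61 / 0.72 / 0.56 |

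The drift toward 1 is general but not uniform. In the last row the prior holds the 12-month estimate near 1, so it first moves away.

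**Step 4: sequential rule.** Trials were simulated with 3-monthly looks from the default trigger (stratum a, variance 25, 400 per IST, 24-month accrual, placebo shared from two other ISTs of the same size). A lift of +1, +1.5 or +2 with no slowing graduated in 44%, 81% and 98% of trials, against about 3% for a null drug. With every participant at 12 months, a +2 lift and a true CPRR of 0.721 gave mean posterior CPRR 0.744 and 0.739, and each graduated in 97%. A test of proportionality at 12 months with 300 per arm would have about 33% power against the +2 lift.

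**Step 5: adding an offset.** With an unscaled term κ ~ N(0, 2²) for j ≥ 1, stratum a and variance 25, the 1.6-point lift gives P(CPRR<0.90) of 0.35 at 12 months and 0.07 at 24. The 12-month figure depends on the prior: 0.52 with SD 1 and 0.28 with SD 4. For a true 25% slowing (κ SD 2), the offset run gives 0.66 at 12 months and 0.99 at 24 in stratum a. In stratum b it gives 0.40 and 0.63, reaching 0.98 only at 48 months. With variance 81, stratum b gives 0.48 at 24 months and 0.83 at 48.

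**The case against.** The SAP says it is unfinished. Section 14 says its assumptions still need justification, and the Executive Summary states the common factor openly as an assumption. The secondary endpoints include the five RBANS indices and twelve subtests that make up the primary score, and each gets an MMRM, so treatment patterns over visits could be examined. An ISA-SAP may add analyses. All of this is true. However, none of it tests the shape of the effect on RBANS total or qualifies the conclusion drawn at graduation, and the minimum success criteria are common to all ISTs.

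The illustration also has limits. Annex I values are starting values for a simplified model. The 300 and 200 participants exceed the trigger size: with 38 active participants and 40 or 12 placebo, the 12-month probability is 0.58 or 0.47. At two visits the two shapes are not identical; they coincide exactly only at a single visit.

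A reader might infer the stronger claim that such a drug graduates early and is then found futile. The documents do not support that as a general result. It needs steep decline and follow-up well beyond 24 months, and follow-up length is left to the ISA. It also needs a moderate lift, roughly 1 to 2.5 points in the stratum a simulations. In stratum b, a +1 lift graduated in 86% of simulated trials but met the futility criterion at 48 months in only 4.5%. In stratum a with follow-up capped at 24 months, a +2 lift never met futility and 68% still met success. Nor does any section say that futility is re-applied after graduation.

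**Conclusion.** The concern holds in this form: the plan equates a CPRR below 0.90 with slowed progression, but the model would return that result for a constant lift as well, and no planned analysis of RBANS total separates the two. For a 1.6-point lift with no slowing, P(CPRR<0.90) at 12 months ranges from 0.61 to 0.91 over the four scenarios in the table. It exceeds 0.85 at 12 months in both strata with variance 25, and in neither with variance 81. These figures rest on the Annex I values, the assumed lift, sample size and late decline, and equal follow-up for everyone.

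Full reversal into the futility range is confined to steep decline with long follow-up. Elsewhere the result is often inconclusive or still a success, so the slowing label would stand uncorrected. The finding concerns what may be concluded from graduation. It does not show that the thresholds or the stopping decision are wrong.

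**What to change.** 1. Add to the Section 14 list, and to the report of each evolution analysis that meets the graduation criterion, a supportive analysis of RBANS total that does not assume proportionality. It has two parts: the BCPM with an unscaled treatment offset for j ≥ 1 beside exp(θ), with sensitivity to the offset's prior SD; and visit-specific treatment differences from an MMRM, already planned for the secondary cognitive endpoints.
2. Reword the Section 18.1 conclusion so that a slowing of 10% or more is stated as conditional on a proportional effect. Report beside it whether the supportive analysis distinguishes slowing from a constant lift.
3. Leave the graduation and futility thresholds and the stopping decision unchanged. Do not make the label depend on passing 0.85 in the offset run. The Step 5 results show that this would withhold the label from true modifiers, in slow decliners even at 24 months.

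The cost is one extra analysis, some SAP text and a weaker claim at graduation. At 12 months the supportive analysis will often not settle the question, and the report should say so. Because stopping is unchanged, the fix does not secure later data where an ISA halts exposure on success.
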